3.3 Characterizing Asthma Severity

Prior to vaccination, it will be necessary to characterize asthma severity and control in each patient (see figures A1 through A3 in the appendix). This characterization will be based on the chart from the National Asthma Education and Prevention Program Expert Panel Report 3 that was issued in October 2007.¹⁷ For the purposes of the study, we will only recruit subjects with persistent asthma and within the full spectrum of severity. Subjects in well-controlled and not well-controlled categories will be enrolled; subjects with very poorly controlled asthma will be discussed with the physician prior to enrollment for their assessment as to whether these subjects can be safely enrolled, based on clinical judgment.

Table 1. Classification of Asthma Severity¹⁷

Lowest level of treatment required to maintain control	Classification of Asthma Severity			
	Treatment of Asthma			
	Intermittent	Mild Persistent	Moderate Persistent	Severe Persistent
Treatment Steps (includes prn SABA use)	Step 1	Step 2 Low dose ICS	Step 3 or 4 Low to Medium dose ICS AND/OR LABA or Montelukast	Step 5 or 6 High dose ICS AND/OR LABA or Montelukast
Additional considerations		Immunotherapy	Immunotherapy plus Asthma specialist	

Abbreviations: SABA: short-acting beta-agonist; LABA: long-acting beta-agonist; ICS inhaled corticosteroids

4 STUDY DESIGN AND PROCEDURES

This is a prospective randomized, open label clinical trial in approximately 50 children aged 5-11 years with a physician diagnosis of persistent asthma. The study will be conducted at three sites: Vanderbilt University Medical Center (Lead site), Cincinnati Children's Hospital Medical Center (contributing site), and Duke University Medical Center (contributing site). Subjects will be randomized 1:1 to receive either a single intramuscular dose of licensed Flucelvax[®] Quadrivalent (ccIIV4) or a single intramuscular dose of licensed Fluarix[®] Quadrivalent (IIV4), stratifying by asthma severity (mild vs. moderate/severe).

4.1 Recruitment

Subject enrollment for this feasibility study will begin during September or October 2016. Site-specific information is described below.

Vanderbilt

Vanderbilt will enroll approximately 20 participants. The Vanderbilt Pediatric Pulmonary Clinic will be the source for the majority of patients enrolled. There are additional Allergy and General Pediatric Clinics that have patients with asthma but if enrolled, these patients will be referred to the Pulmonary Clinic or to the Clinical Research Center at the Children's Hospital where enrollment will occur.

The Pediatric Pulmonary Clinic has the necessary space and infrastructure to provide support for this study. Ongoing clinical research is conducted there and the investigators can integrate research enrollment in the same area as they are providing clinical care. During the months prior to enrollment, the research staff will inquire about the study interest, will assess the ability of the families to assess clinical symptoms and to perform home respiratory testing, and will identify parental preferences for recording reaction data. Drs. [name] and [name] will facilitate introduction of the patients to the study staff, and the patients will be informed about the study. During August and September 2016, when recruitment and enrollment is expected to begin, Vanderbilt Vaccine Research Program (VVRP) study staff will be actively involved in recruitment. All qualifying patients for the study will be given information and contact numbers to discuss the study in the months prior to the study onset. The research team will provide follow up contact information to discuss questions or concerns.

After informed consent, Vanderbilt study staff will target subjects with moderate or severe persistent asthma for the conduct of the study, which represents the majority of patients at this Vanderbilt clinic. Using the Severity and Control tables shown in the Appendix, subjects will be graded for each of these two parameters, severity and control, and these assessments will be recorded on the Case Report Form. Lists of children with an interest in the study will have been previously compiled prior to the availability of the vaccine. If the parents agree to participation, then the subjects will be seen in the outpatient clinic areas (e.g., Pediatric Pulmonary Clinic or Pediatric Clinical Research Center) at Vanderbilt Children's Hospital.

Cincinnati

Cincinnati will enroll approximately 20 participants. The study population will be children with asthma who are patients at Cincinnati Children's Hospital Medical Center (CCHMC) with primary recruitment from the Pulmonary Asthma and Pediatric Primary Care (PPC) Clinics at CCHMC. One of the ongoing quality management goals at CCHMC is to document the level of severity for all children cared for at CCHMC with

asthma. Of those not categorized, Cincinnati will be able to categorize their asthma severity and control if they interested in the study.

If influenza vaccine (ccIIIV4 and IIV4) is available, Cincinnati would like to start enrollment in September 2016 to maximize the number of weeks for enrollment. Using local and national data, we will determine the target weeks for enrollment to ensure this high-risk group of children with asthma are vaccinated for influenza well before the influenza season starts. The target enrollment period should be as soon as both vaccines are available and should end by the last week of November allowing for approximately 12-13 weeks for enrollment.

Cincinnati will recruit approximately 20 children, 5-11 years of age, diagnosed with asthma of varying degrees of severity. The primary strategy for recruitment will be through the Pulmonary Asthma Clinic and the Pediatric Primary Care Center. Cincinnati will advertise at these two sites, as well as through the asthma registry and their database of past research participants who have agreed to be e-mailed for future studies. Any written communication provided to the potential subjects' parents/legal guardians about the study will be submitted to the IRB for their approval before study initiation. Recruitment letters introducing the study will be sent to parents of asthmatic children shortly ahead of the influenza vaccination season. To assist with recruitment, parents will then be called 2 to 3 weeks after sending the letter to screen for interest, eligibility and enrollment (September-November 2016). Recruitment will also be coordinated with well child visits and clinic visits. Recruitment will be advertised by the use of flyers posted in pediatric/allergy/and pulmonary clinics.

Interested parents may call or email the Cincinnati study line and study personnel will discuss the study by phone or email with the parent. Subjects will be screened using a phone screening tool (eligibility and brief medical history questions) from the parents. If potentially eligible and interested, an appointment will be scheduled. Parents will be informed that their decision to participate or not to participate in the study will not have any effect on their child as a patient. If parental permission is given for participation, the subjects will be seen in the Research Clinic (Schubert Center) at Cincinnati Children's Hospital Medical Center. Cincinnati will enroll approximately 20 children with persistent asthma to include approximately 50% with mild, persistent asthma and 50% with moderate to severe asthma.

Duke

Duke will enroll approximately 10 children age 5-11 years with persistent asthma. Duke study staff will obtain informed consent from parents/guardians of children with persistent asthma at clinical sites affiliated with Duke University in order to enroll, randomize and vaccinate approximately 10 children (5 with moderate to severe asthma and 5 with mild asthma). Children with persistent asthma will be enrolled at Duke Allergy/Immunology and Pulmonary Clinics located at Duke Children's and WakeMed Children's Specialty Services in Raleigh, NC.

Identification of children with persistent asthma will occur from providers at the clinic and through the use of the Duke patient data portal. With permission of their health care provider, recruitment letters introducing the study may also be sent to parents of asthmatic children. To assist with recruitment, parents will then be called 10 days after sending the letter to schedule children for screening and enrollment. Recruitment will also be

[figure not shown]
coordinated with clinic visits and or vaccination clinics. Recruitment will be advertised by the use of flyers posted in allergy/and pulmonary clinics.

At all sites, study participants will be compensated for each clinic visit (including enrollment) and for each follow-up telephone/email contact.

4.2 Enrollment/Randomization

In total, the study will enroll approximately 50 children between 5-11 years of age, inclusive, who have persistent asthma of varying levels of severity (~20 from Vanderbilt, ~20 from Cincinnati and ~10 from Duke). The study will aim to enroll equal proportions of participants (50%) with mild and with moderate/severe asthma.

Subjects will be randomized 1:1 to receive by intramuscular injection either a single dose of a licensed non-egg, cell culture-based, quadrivalent inactivated influenza vaccine (cclIV4-Flucelvax® Quadrivalent) or an egg-based formulation of inactivated influenza vaccine, stratifying by asthma severity (mild vs. moderate/severe). Randomization will be done separately for each site. Each site may have more than one clinic to recruit participants, and proportions of participants with mild or moderate/severe asthma can vary by clinics, but the targeted proportions of asthma severity at site level will be 50% for each. Therefore, overall enrollment with randomization will recruit the same proportions of asthma severity participants in each arm. Randomization will be accomplished using the REDCap System, hosted at Vanderbilt. Since this is a web-based system, it is easily accessible to the other collaborating sites as well.

4.3 Study Visits and Procedures

4.3.1 Visit 1 (Day 1) - Enrollment and Vaccination

- Informed consent/assent will be obtained
- Medical history and medication history will be obtained, including a review of all current medications and medications taken within 28 days of enrollment.
- History of asthma and allergy disease (asthma triggers, environmental, food and other documented allergies, allergy testing results, household pets, exposure to secondhand smoke in the home or daycare or where subject spends considerable time during the day) will be captured.
- Temperature will be recorded prior to immunization; oral temperature must be <100.4° F prior to administration of vaccine.
- Height and weight will be measured in order to calculate subject's BMI
- Eligibility criteria will be reviewed to determine if child meets criteria for study
- Asthma severity and control will be assessed
 - Clinical assessment to assess baseline asthma clinical symptoms [**Preventative Omalizumab or Step-up Therapy for Severe Fall Exacerbations (PROSE) asthma symptom questionnaire**]
 - Administration of the Childhood Asthma Control Test (cACT)
- Patient and parent(s)/guardian will be taught proper peak flow technique and will be provided with a peak flow meter by the study staff, even if they have another peak flow meter at home. A baseline peak flow measurement (standing, three attempts) will be collected. The patient (and parent/guardian) will be requested to use this same peak flow meter every day at home beginning on the day of vaccination and for 14 days following vaccination, and on day 43 after vaccination (days 1 through 15 and on day 43, respectively). (see section 4.7 below)
- The child will be randomized to the respective treatment group (ccIIV4 or IIV4) using the REDCap System. The Vaccine Information Sheet (VIS) for the respective vaccine administered will be provided to parents/guardians before the vaccine is administered. The VIS will be in the primary language of the parent/guardian consenting for the child to be enrolled in the study.
- The vaccine will be administered according to the study randomization scheme.
- Memory aid (daily symptom and peak flow diary on vaccination day, Day 1, and for the next 14 days, through Day 15, and on day 43) will be reviewed with the parent and the parent will demonstrate ability to take temperature and will be instructed in the collection of post-vaccination asthma clinical symptoms and symptom scores, adverse event, fever and concomitant medication administration data for 14 days (until day 15) after vaccination
- Parent/guardian will be given a thermometer and a ruler to use for daily temperature and local reactions recording, respectively
- Study staff will record any immediate adverse events (AEs) after vaccination occurring while still in the clinic
- Study staff will educate the family to notify the study staff if the patient requires an additional unscheduled medical visit for management of asthma symptoms (medical services utilization) or a new asthma control medication that has been prescribed.

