4.9 Monitoring Vaccine Safety in the First 15 Days

On the vaccination day and for the next 14 days post-vaccination, all subjects will be monitored daily by their parents and the information will be recorded using memory aids provided at the enrollment visit. Daily reactogenicity, including measurement of nighttime awakening, and two asthma scoring systems will be completed (cACT score and the PROSE score).

In addition to the two symptom scores above, several predefined events that could occur after vaccine administration will also be recorded for 14 days after vaccination. These will include; fever (oral temperature $\geq 100.4^{\circ}\text{F}$), runny nose/ nasal congestion, sore throat, cough, wheeze, vomiting, change in activity level, appetite change, irritability, abdominal pain/stomachache, headache, chills, and muscle aches. Local reactions after the intramuscular vaccination will also be captured and include: redness, swelling, and/or pain around the injection site. Medication receipt, new prescriptions for asthma medications, and any previously unscheduled healthcare utilization (medical office visits, ED visits, hospitalizations) will also be documented on the reaction form. To ensure compliance with the reaction assessment, parents will be called or emailed through REDCap on Days 4, 8 and 15 by the study staff.

On the day of vaccination and during the first 14 days after vaccination, if the subject reports an increase in their symptoms and an increase in the need for medications for their asthma, the family will be instructed to contact the study staff, so medical records can later be collected, if applicable. If at any point a study participant is experiencing symptoms of any asthma exacerbation, the participant or their parent will be instructed to contact their PCP and inform study staff of this encounter.

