7.2 Termination of Study

This study may be terminated for safety concerns of the PI, CDC, or participating IRBs.

8 Statistical Analytic Plan

This study aims to enroll approximately 50 participants (~20 from Vanderbilt, ~20 from Cincinnati and ~10 from Duke). Since sample-sizes were predetermined and since this is a feasibility study, no power calculations were conducted. All analyses will be performed using R 3.2.3 (r-project.org), SAS version 9.4, or STATA version 14.

Feasibility Analysis

The proportion of children meeting the outlined feasibility benchmarks (Appendix, Table A1) will be determined.

Descriptive Statistics

Descriptive analyses will be summarized for continuous variables with mean, standard deviation, median, and interquartile range. Categorical variables will be summarized with frequencies and percentages. Explanatory figures will be generated to evaluate the data distribution. Comparisons of demographic characteristics between cclIV4 and IIV4 groups will be conducted using Pearson Chi-square and Wilcoxon tests appropriately.

Primary Objective

To assess the feasibility of conducting a randomized prospective safety study of LAIV4 versus IIV4 during the 42 days after vaccination in children aged 5-11 years with persistent asthma of varied severity (cclIV4 will be used as a surrogate for LAIV4)

Primary Outcomes Measures

1. Assess the proportions of those achieving Feasibility Benchmarks (Table A1 Appendix)
2. Qualitatively describe best practices and lessons learned

Secondary Objectives

1. To compare proportions of local and systemic reactogenicity events during the 14 days after cclIV4 versus IIV4 in children with asthma aged 5-11 years.
2. To describe the unsolicited and serious adverse events in children receiving cclIV4 and IIV4 during the 42 days.
3. To compare proportions of asthma exacerbations during the 14 days after cclIV4 versus IIV4 in children with asthma aged 5-11 years.
4. To compare proportions of asthma exacerbations during the 42 days after cclIV4 versus IIV4 in children with asthma aged 5-11 years.
5. To explore differences between the cclIV4 and IIV4 groups regarding clinical asthma symptoms after vaccination and changes in asthma control before and after vaccination in children with asthma of varied levels of severity.

Secondary outcome measures

1. Proportion of subjects with solicited local and systemic reactogenicity events for 14 days after vaccination between recipients of cclIV4 and IIV4.

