APPENDIX

[figure not shown]
Figure A1. Asthma Control Chart for Children 5-11 years of age¹⁷

Asthma Control Chart

FIGURE 3-5b. ASSESSING ASTHMA CONTROL IN CHILDREN 5–11 YEARS OF AGE

Components of Control		Classification of Asthma Control (Children 5–11 years of age)		
		Well Controlled ≤2 days/week but not more than once on each day	Not Well Controlled >2 days/week or multiple times on ≤2 days/week	Very Poorly Controlled Throughout the day
Impairment	Symptoms			
	Nighttime awakenings	≤1x/month	≥2x/month	≥2x/week
	Interference with normal activity	None	Some limitation	Extremely limited
	Short-acting beta ₂ -agonist use for symptom control (not prevention of EIB)	≤2 days/week	>2 days/week	Several times per day
	Lung function • FEV ₁ or peak flow • FEV ₁ /FVC	>80% predicted/ personal best >80%	60–80% predicted/ personal best 75–80%	<60% predicted/ personal best <75%
Risk	Exacerbations requiring oral systemic corticosteroids	0–1/year	≥2/year (see note)	
	Consider severity and interval since last exacerbation			
	Reduction in lung growth	Evaluation requires long-term followup.		
	Treatment-related adverse effects	Medication side effects can vary in intensity from none to very troublesome and worrisome. The level of intensity does not correlate to specific levels of control but should be considered in the overall assessment of risk.		

Key: EIB, exercise-induced bronchospasm; FEV₁, forced expiratory volume in 1 second; FVC, forced vital capacity; ICU, intensive care unit

Figure A2. Daily Medication Steps for Persistent Asthma¹⁷

Key: Alphabetical order is used when more than one treatment option is listed within either preferred or alternative therapy. ICS, inhaled corticosteroid; LABA, inhaled long-acting beta₂-agonist, LTRA, leukotriene receptor antagonist; SABA, inhaled short-acting beta₂-agonist

Notes:

- The stepwise approach is meant to assist, not replace, the clinical decisionmaking required to meet individual patient needs.
- If alternative treatment is used and response is inadequate, discontinue it and use the preferred treatment before stepping up.
- Theophylline is a less desirable alternative due to the need to monitor serum concentration levels.

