Education provided at first visit is understandable	Before leaving the clinic, all parents or guardians will demonstrate: 
 • proper use and care of the digital peak flow meter • proper use and care of oral digital thermometer • proper use of study ruler to assess erythema and induration • proper use of paper and/or electronic data entry forms
Memory Aid Data Completion through Day 15	At least 80% of the patients will complete the memory aid for 11 of the 15 day monitoring period
Memory Aid Data Completion Day 16 through day 43	At least 70% of the patients will complete the memory aids for Day 16 through 43
Peak Flow measurements (early study)	At least 75% of subjects will perform and document all home digital peak flow measurements (per protocol) for on at least 11 of the 15 day monitoring period.
Peak flow measurement (late study)	At least 70% of subjects will perform and document the digital peak flow for Day 42.
Nighttime awakenings (done in am)	At least 70% of subjects will document nighttime awakenings for at for on at least 11 of the 15-day monitoring period.
Day 4 (-1 to +2) call	At least 80% of study subjects will respond to Day 4 call and provide requested data (ACT and Prose are administered on the call)
Day 8 (± 2) call	At least 80% of study subjects will respond to Day 8 call and provide requested data. (ACT and Prose are administered on the call)
Day 15 (-1 to +2) call	At least 80% of study subjects will respond to Day 15 call and provide requested data. (ACT and Prose are administered on the call)
Day 29 (± 2) call	At least 70% of study subjects will respond to Day 29 call and provide requested data.
Day 44 (+3) call	At least 70% of study subjects will respond to Day 44 call and provide requested data. (ACT and Prose are administered on the call)
Parental Satisfaction survey	At least 70% of parents will complete the Parent/Guardian satisfaction survey

Schedule of Events

Table A2.

Study Visit	Enrollment Visit 1 (Vaccination)	Visit 2	Visit 3	Visit 4	Visit 5	Visit 6
Study Day	1	4	8	15	29	43
Visit Window (Days)	n/a	3-6	7-9	14-17	27-31	44-47
Type of Visit	Clinic	Call/email	Call/email/clinic ^a	Call/email	Call/email	Call/email
Obtain Informed Consent	X					
Obtain Assent (if applicable per site's IRB requirement)	X					
Review Eligibility Criteria	X					
Document Prior Year Flu Vaccination	X					
Review Medical History	X					
Review Asthma History	X					
Assess asthma clinical symptoms ^b (PROSE)	X	X	X	X		X

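### The plan describes no item-level pre-vaccination reading of the non-fever diary symptoms, and outcomes 1 and 5A have no rule separating continuing symptoms from new or worsened ones.

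*Combined protocol and SAP*

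**What the plan says.** Before the injection, Section 4.3.1 records oral temperature, a baseline PROSE asthma symptom questionnaire, the cACT and a baseline peak flow. Medical, asthma and allergy history are also taken. Exclusion criterion 1 defers or excludes a child with acute illness or fever in the 72 hours before enrollment.

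The memory aid runs from vaccination day (Day 1) through Day 15. At Visit 1 the parent "will be instructed in the collection of post-vaccination asthma clinical symptoms and symptom scores, adverse event, fever and concomitant medication administration data". Section 4.9 says that "several predefined events that could occur after vaccine administration will also be recorded for 14 days after vaccination". Its systemic list covers fever, nasal symptoms, sore throat, cough, wheeze, vomiting, activity, appetite, irritability, abdominal pain, headache, chills and muscle aches. Table A2 has no row for a pre-injection reading of these items.

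In Section 8, outcome 1 is the "Proportion of subjects with solicited local and systemic reactogenicity events for 14 days after vaccination", compared between arms. Outcome 5A is a yes/no proportion for each asthma symptom on the memory aid over Days 1 to 15, with a 95% CI for the difference. Neither mentions baseline. Outcomes 5B, 5C and 5D (PEFR, cACT, PROSE) are each defined as change from a pre-vaccination value.

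**The concern.** Every child has persistent asthma, and Section 3.3 states that "Subjects in well-controlled and not well-controlled categories will be enrolled". Figure A1 puts the symptom criterion for the second of these groups at ">2 days/week or multiple times on ≤2 days/week". Cough, wheeze or rhinitis on the day of vaccination is therefore plausible in some children. The 72-hour rule addresses acute illness, not chronic symptoms.

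If such a symptom continues after the injection, outcomes 1 and 5A as written count it as a post-vaccination event. Tabulating by day of onset would not help, because a continuing symptom would appear as starting on Day 1. The per-arm proportions would then mix background with new events, and a real difference between vaccines would be harder to see. The protocol's background section says the findings are meant to improve a later LAIV4 study, in which wheeze is a central safety question, so the diary method matters beyond this trial.

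Injection-site redness, swelling and pain are not affected.

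**Working it through.** The plan states no event rate or power figure for these outcomes, so there is nothing of its own to reproduce. The check has two parts.

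**1. Readings and their use, side by side**

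| Item | Pre-vaccination reading described | Used in outcome 1 or 5A |
|---|---|---|
| Fever | Yes, oral temperature | No rule stated |
| Asthma symptoms as a domain | Yes, PROSE and cACT | No; used in 5C and 5D |
| Cough and wheeze as diary items | None described | No rule stated |
| Nasal symptoms, sore throat, headache and the other items | None described | No rule stated |

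The covariate list in Section 8 names baseline daytime and nighttime asthma scores and nighttime awakening, so some baseline symptom data are intended. That list serves the models and does not enter the proportions in outcomes 1 and 5A.

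**2. Illustration of size**

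Inputs from the plan: about 50 children, and "Subjects will be randomized 1:1 to receive either a single intramuscular dose", so about 25 per arm. Inputs assumed: prevalence *b* of a symptom present before vaccination and continuing afterwards (10% to 50%), and new-event risk *a* in each arm.

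Observed proportion = 1 − (1 − b)(1 − a). Observed difference = (1 − b)(a₁ − a₂). Power is the normal approximation for two proportions, two-sided 5%, 25 per arm.

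| b | Observed if a = 10% | Observed if a = 30% | Difference (points) | Power |
|---|---|---|---|---|
| 0 | 10% | 30% | 20 | 42% |
| 10% | 19% | 37% | 18 | 29% |
| 20% | 28% | 44% | 16 | 21% |
| 30% | 37% | 51% | 14 | 17% |
| 50% | 55% | 65% | 10 | 11% |

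Example at b = 30%: 1 − 0.7 × 0.9 = 0.37 and 1 − 0.7 × 0.7 = 0.51. With equal risks in both arms the expected difference is 0 at every *b*.

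Chance imbalance in pre-existing symptoms between arms has standard deviation √(2b(1 − b)/25). At b = 30% this is √(2 × 0.3 × 0.7/25) = 0.13, or 13 percentage points. Without a baseline row that imbalance cannot be seen.

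**3. Limit of the illustration**

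The table holds for symptoms that continue. Suppose instead that a symptom comes and goes, independently from day to day. The chance of at least one report in 15 days is then 1 − 0.85¹⁵ = 91% at 15% per day, and 1 − (5/7)¹⁵ = 99% at two days per week, whatever the baseline day showed. Take children free of the symptom at baseline, 15% background per day, and added risks of 10% and 20%. A new-onset rule gives 1 − 0.0874 × 0.9 = 92.1% against 1 − 0.0874 × 0.8 = 93.0%, a relative risk of about 1.01. One look-back does little for such symptoms.

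**The case against.** The best case for the plan is this. Visit 1 does take pre-vaccination readings: temperature, PROSE, cACT and peak flow. Within-child change in asthma status is analyzed in 5B to 5D. Randomization, stratified by severity, gives both arms the same expected background, and the comparator arm shows it. The outcomes are secondary, and Section 8 says "Since sample-sizes were predetermined and since this is a feasibility study, no power calculations were conducted". The memory aid and the PROSE and cACT items are not reproduced, so the form may already have a pre-injection column.

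Much of this stands. A reader might infer that no solicited symptom is read before vaccination. The documents contradict that for fever and for asthma symptoms as a domain. A reader might also infer that old symptoms are classed as vaccine reactions, but the plan attributes no individual report to vaccine. It counts them as events after vaccination.

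A third tempting step is to turn Figure A1's cut-offs into a Day 1 prevalence of 29% to 43% (2/7 to 3/7). A true relative risk of 2.0 (20% against 10%) would then shrink to 1.20 or 1.12, and a new-onset rule would cut the variance 2.5 to 3.2 times. The documents do not support this. The cut-offs classify asthma control and are not prevalence data. They say nothing about headache or runny nose. The calculation also treats symptoms that recur weekly as a one-time Day 1 state, which the third step of the working shows to be wrong.

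The objection does not remove the gap. Randomization does not undo inflated per-arm proportions, dilution or unseen chance imbalance. No section links PROSE, cACT or temperature to outcomes 1 and 5A. If the form has a baseline column, the analysis rule is still missing.

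**Conclusion.** The point holds as a modest design gap. No item-level baseline is described for the non-fever systemic diary items, and outcomes 1 and 5A do not separate continuing symptoms from new or worsened ones. The likely effect is higher proportions in both arms and a diluted contrast, with no expected bias toward either arm.

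The size cannot be stated, because the documents give no background prevalence. The tabulated figures rest on assumed rates, about 25 children per arm and symptoms that continue; they are illustrations only. The feasibility benchmarks, which are the primary outcome, do not depend on this gap. The change is still worth making, because it is cheap and this trial is meant to test methods for a later safety study.

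**What to change.** In Section 4.3.1, have the parent complete the systemic memory-aid symptom items once, for a short stated look-back such as the preceding 24 hours, and store this as a baseline row. Do it before randomization, because the study is open label and the vaccine-specific information sheet is handed over before the injection. It can double as the demonstration of "proper use of paper and/or electronic data entry forms" in Table A1. Section 4.3.1 lists the memory-aid review after the injection, so that part of the training would move forward. Add the row to Table A2.

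In Section 8, for outcomes 1 and 5A, report the proportion of children with each item absent at baseline or worse than baseline, beside the all-reports proportion. State the denominator. For continuing symptoms that do not worsen, the difference over all children stays at (1 − b)(a₁ − a₂); only among children free of the item at baseline does it return to a₁ − a₂. Tabulate baseline presence by arm.

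The cost is about a minute at Visit 1, one diary column and a line or two of SAP text. A symptom that recurs at its baseline level drops out of the new-or-worsened figure, which is why both figures are shown. One look-back identifies continuing symptoms, but not intermittent ones that were absent then.
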